5. Treatment with Tofacitinib for 16 weeks in people with DS will result in statistically significant improvement in quality of life measured by one or more NIH PROMIS tools.
6. Treatment with Tofacitinib for 16 weeks in people with DS will result in statistically significant improvement in one or more measures of cognitive function.

II. Background and Significance:

Trisomy 21 (T21) is the most common human chromosomal disorder, occurring in ~1/700 live births, leading to the condition known as Down syndrome (DS) (1, 2). A remarkable observation enabled by the significant increase in the life expectancy of people with DS is that T21 causes a novel disease spectrum, protecting these individuals from some diseases, such as most solid tissue tumors (3, 4), while strongly predisposing them to others, such as Alzheimer's disease (5). Importantly, people with DS have an unequivocally high

prevalence of widespread immune dysregulation. In fact, they are likely to be the largest human population with a genetic predisposition to multi-organ autoimmunity. Multiple conditions driven by autoantibodies and autoreactive T cells show significantly elevated incidence among individuals with T21, including autoimmune thyroid disease (AITD) (6-12), celiac disease (13-19), and type 1 diabetes (20-22). Importantly, and directly related to the clinical outcomes to be evaluated in this trial, many immune skin conditions are also more prevalent in T21, including atopic dermatitis (AD), alopecia areata (AA), hidradenitis suppurativa (HS), psoriasis, and vitiligo (23-26).

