
Participants who have a previous diagnosis of psoriatic arthritis (PsA), or who have a suspected diagnosis of arthropathy/arthritis, who have had hand radiographs in the past 12 months will be asked to release copies using the medical record release form. Participants with PsA will also have additional observational skin assessments, including the Fingernail Assessment. The Disease Activity Score 28 (DAS28) will be collected at Visits 2, 5, 7, and 10E. Tofacitinib is an FDA-approved treatment for PsA.

Cognitive tests, including the Leiter 3 Sustained Attention, Nonverbal Stroop Tasks, Forward/Backward, and Sequential Order; the CANTAB Paired Associate Learning, Spatial Span, and Reaction Time; the NEPSY II Visuomotor; the KBIT II; the PPVT 5 Form A; SRT; and the SALT story elicitation task will be performed, and video recorded at the baseline and 16-week visits, and at 40 weeks for those in the Extension Arm. In addition, the DLQI and NIH PROMIS quality of life measures Emotional Distress-Anxiety Short Form 4a,

[figure not shown]

Figure 6. Timeline of proposed clinical activities.

Emotional Distress-Depression Short Form 4a, Cognitive Applied Cognitive General Concerns Short Form 4a, and Pediatric Positive Affect Short Form 4a will be administered at the baseline and 16-week visits (*Figure 6*) and 40 weeks.

Our team will collect specimens for research purposes at the screening, baseline, 2-, 8-, 16-, and 2-week post-treatment visits (*Figure 6*). These specimens include a tongue swab and additional tubes from the scheduled blood draw to support the battery of immune dysregulation analyses described in *Research Methods for Specific Aim 2* below, including DNA. Non-invasive skin tapes will be collected at baseline, 8-, and 16-weeks. All collected samples and laboratory results, such as autoantibody results, that remain unused at the end of the study or do not directly relate to the defined endpoints will be banked for future unspecified research purposes related to the goal of this study, including the possible generation of cell lines. As additional needed analyses are defined, this protocol will be amended. Research samples collected are outlined in Table 3. Participants in the Extension Arm (see below) will have the above research specimens collected at E28 and E40 as well, with the exception of skin tapes, which are only collected at E40.

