From a dermatology standpoint, this trial is considered a 'bucket trial', so designated because we will include individuals with DS and diverse active immune skin conditions. We aim to enroll at least 10 participants during the initial phase, before performing a qualitative interim analysis and continuing with 30 additional participants. Up to 15 participants may be included in the interim analysis. Based on our ongoing cohort study and epidemiological data of skin diseases in people with DS (24, 25, 116-118), we expect to enroll five predominant conditions: AD, AA, HS, psoriasis, and vitiligo (*Figure 1B*), but will accept other immune skin conditions according to our dermatologists' expertise. Being an open-label, proof-of-concept study, all participants will receive Tofacitinib at 5mg BID for 16 weeks. We will evaluate changes from baseline to 16 weeks in: 1) Investigator's Global Assessments (IGAs), 2) Dermatology Life Quality Index (DLQI) (119), and 3) Disease-specific metric scores. The IGA and DLQI will serve as 'composite endpoints' to capture overall clinical improvement in a disease-agnostic fashion. Additionally, each participant will be monitored using the relevant accepted disease-specific metric scoring systems, for example: Eczema Area and Severity Index (EASI) for AD, Severity of Alopecia Tool (SALT) for AA, Modified Sartorius Score (MSS) for HS, Psoriasis Area and Severity Index (PASI) for psoriasis, and Vitiligo Extent Tensity Index (VETI) for vitiligo (120-124).

These measures are all well-validated and widely used in clinical trials related to skin disease, and our team of dermatologists has extensive experience with all these metrics. We define success of this endpoint as statistically significant *percentage reduction* in a) IGA values, b) DLQI values, and c) disease-specific scores between baseline and 16 weeks as defined by a two-sided, paired Student's t-test.

Research Methods for Specific Aim 4. To characterize the impact of JAK inhibition on cognition and quality of life in Down syndrome.

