Subdomains from the Leiter-3 International Performance Scale will be used to assess executive function including inhibitory control (Sustained Attention), working memory (Forward and Backward Memory), and cognitive flexibility (Nonverbal Stroop Tasks), as well as spatial processing (Sequential Order). The Leiter 3 is a lifespan nonverbal measure of cognition, attention, and neuropsychological function and was normed on individuals ages 3 to 75 years. This measure was endorsed by the NIH Working Group (125), and it is considered to be a phenotype-sensitive measure for individuals with DS because it involves minimal receptive language, and no expressive language, demands. Subdomains from the CANTAB (126) will be used to assess episodic memory (Paired Associate Learning), spatial processing (Spatial Span), and processing speed (Reaction Time Interval). An additional Simple Reaction Time test will be administered from the science of behavioral change website. The SALT story elicitation task has been added to capture expressive language. The NEPSY II Visuomotor will assess motor control. In addition, the KBIT II and PPVT 5 are included as control measures of overall development status and vocabulary. This battery takes into consideration length of time required for administration, its suitability for individuals with varying degrees of cognitive ability, and previous experience of our team in terms of participant acceptability. This short test battery will be administered and video recorded at baseline blood draw (+/- 3 days), and again at 16 weeks of treatment and at E40 for those in the Extension Arm. We define success of this endpoint as statistically significant improvement in any one of the cognitive measures described above between baseline and 16 weeks as defined by a Wilcoxon signed-rank test with FDR correction or a two-sided, paired Student's t-test with FDR correction, as appropriate.

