Endpoint Definition: A statistically significant *percentage reduction* in one or more metrics of skin pathology, including: a) IGA values, b) DLQI values, and/or c) disease-specific scores between baseline and 16 weeks as defined by a two-sided, paired Student's t-test.

Method: The first endpoint for this Specific Aim will be to monitor changes in the Investigator's Global Assessment (IGA), which is a well-established, disease-agnostic measurement of skin disease severity that employs a continuous visual analog scale and has good test-retest reliability. A second disease-agnostic secondary endpoint will be the Dermatology Life Quality Index (DLQI), a patient-reported outcome that is commonly used in dermatology trials. The third secondary endpoint for this study is a percentage reduction in the disease-specific measurements used to monitor each skin condition. We will employ Eczema Area and Severity Index (EASI) for AD, Severity of Alopecia Tool (SALT) for AA, Modified Sartorius Score (MSS) for HS, Psoriasis Area and Severity Index (PASI) for psoriasis, and Vitiligo Extent Tensity Index (VETI) for vitiligo. By focusing on a *percentage reduction* in disease-specific scores, we will be able to compare values from participants with different conditions. In every case (IGA, DLQI or disease-specific scores) we will define whether the percentage reduction reaches significance using a two-sided, paired Student's t-test comparing baseline and 16 weeks of treatment. In every case, for 40 individuals, we have 80% power to detect an effect size of 0.45 with a p-value less than 0.05, as calculated by G*Power software. Finally, although we will be analyzing changes between baseline and 16 weeks, data will be also gathered at the intermediate time point of eight weeks for research purposes.

Specific Aim 4. To characterize the impact of JAK inhibition on cognition and quality of life in Down syndrome.

Tertiary Endpoint: Change in any one or more of the cognitive assessments performed.

Endpoint Definition: a statistically significant improvement in any one of the cognitive measures employed between baseline and 16 weeks as defined by a Wilcoxon signed-rank test with FDR correction or a two-sided, paired Student's t-test, as appropriate.

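### The cognitive success rule can be met by a practice gain alone, and the plan would read that gain as an effect of tofacitinib

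*Combined protocol and SAP*

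**What the plan says.** Section IV.C, Research Methods for Specific Aim 3, sets the design: "Being an open-label, proof-of-concept study, all participants will receive Tofacitinib at 5mg BID for 16 weeks". No group is tested without the drug.

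Section IV.C, Research Methods for Specific Aim 4, sets the schedule: "This short test battery will be administered and video recorded at baseline blood draw (+/- 3 days), and again at 16 weeks of treatment". A third testing, at week 40, exists only for Extension Arm participants. The success rule is "We define success of this endpoint as statistically significant improvement in any one of the cognitive measures described above between baseline and 16 weeks", and the sentence goes on to require a Wilcoxon test "with FDR correction or a two-sided, paired Student's t-test with FDR correction, as appropriate". Section VII, Specific Aim 4, repeats the rule as "a statistically significant improvement in any one of the cognitive measures employed between baseline and 16 weeks as defined by a Wilcoxon signed-rank test". There the definition attaches the correction only to the Wilcoxon test, but the method paragraph below it gives FDR-corrected p-values for both Leiter 3 and CANTAB.

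The claim is causal. Hypothesis 6 in section I says that treatment "will result in statistically significant improvement in one or more measures of cognitive function". Section VII says that these endpoints serve to determine the drug's impact on cognition, and it labels them exploratory and tertiary.

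The Aim 4 list holds 12 measures: four Leiter 3 subtests, three CANTAB subtests, NEPSY II Visuomotor, PPVT 5, KBIT II, SRT and the SALT story task. Of these, the same section says that "the KBIT II and PPVT 5 are included as control measures of overall development status and vocabulary".

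**The concern.** A second attempt at timed, memory or attention tasks can be better than the first through familiarity with the task. With no untreated retest group, the test on each measure asks whether mean change is zero, whereas hypothesis 6 asks whether the drug caused the change. The two questions coincide only if retest alone produces no mean change.

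The available text has no provision for this: no alternate forms (PPVT 5 is named as Form A only), no familiarisation session before baseline, no reliable-change threshold and no practice-adjusted null. Test-retest reliability is named as a selection criterion, but a reliable test can still shift upward on average at retest. The Aim 4 part of section VI discusses effects that might be missed and tasks that might not be completed. It does not discuss gains that are not due to the drug.

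At stake is a reported cognitive benefit of JAK inhibition in Down syndrome that could be a retest gain. The rule as worded also lets one of the two control measures carry that conclusion alone.

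**Working it through.** **Inputs.** n = 40 completers (section IV.C, Recruitment and Pre-Screening; section VII uses 40 for the other endpoints with the same 0.45). Two-sided 5% tests with FDR correction (sections IV.C and VII). Twelve measures (Aim 4 list). Assumed, because the documents do not give them: the size of the practice gain, the correlation between change scores, and Benjamini-Hochberg at 5% over all 12 as the FDR procedure and family.

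**Step 1: the plan's own figure.** For a paired t-test, power is the upper tail of a noncentral t with n−1 degrees of freedom and noncentrality d√n. With d = 0.45 and n = 40, the noncentrality is 0.45 × 6.325 = 2.846 on 39 degrees of freedom, and power is 79.3%. This agrees with the stated 80%, although only at an unadjusted 0.05.

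**Step 2: the same formula with an inert drug.** The test does not know the source of d. If d is a pure practice gain, in SDs of the change score, the chance of a significant improvement on one measure at unadjusted 0.05 is:

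| Practice gain d | 0 | 0.1 | 0.2 | 0.3 | 0.4 | 0.5 |
|---|---|---|---|---|---|---|
| Chance | 2.5% | 9% | 23% | 46% | 69% | 87% |

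The stated 80% power at 0.45 is therefore also about 80% power to declare success on a practice gain of that size.

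**Step 3: the rule as written, with FDR.** Change scores for 40 participants on 12 measures were simulated with SD 1, a common correlation and no drug effect. Each measure was tested by paired t-test (a simplification, since Leiter 3 is to use the Wilcoxon test), and Benjamini-Hochberg was applied at 5%. A trial counts as a success if at least one rejected measure moved in the favourable direction.

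| Practice gain on all 12 | 0 | 0.1 | 0.2 | 0.3 |
|---|---|---|---|---|
| Correlation 0.3 | 2.4% | 12% | 37% | 71% |
| Range, correlation 0 to 0.5 | 2.0–2.6% | 10–14% | 30–48% | 60–89% |

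If only two of the 12 measures gain (correlation 0.3), the chance is 10%, 27% and 51% at 0.2, 0.3 and 0.4 SD. The family size matters little: with eight measures all gaining (correlation 0.3), the figures at 0.1, 0.2 and 0.3 are 12%, 35% and 69%.

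The first column shows what FDR does. It holds false success near 2.5% when true retest change is zero. The other columns show that it does not remove a systematic shift.

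**Step 4: the control measures.** Section IV.C refers to the measures described above, and section VII to those employed. Both phrases take in KBIT II and PPVT 5, which are in the list and are given at both visits. The Outcome Measures section does not list either one, but neither success definition limits itself to that section. A significant gain on vocabulary alone would meet the rule.

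**The case against.** The strongest reply is that this is a limit of any single-arm study, shared by the skin and PROMIS endpoints. The cognitive endpoints are tertiary, are called exploratory, and enter neither a primary endpoint nor a stopping rule. That stands and limits the severity. It does not justify a causal success rule that familiarity can satisfy, when a change of wording would cure it.

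Several stronger readings are tempting but not supported:

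- A reader might infer that any numerical gain counts. It does not: the gain must be significant after FDR correction. A calculation without correction overstates the risk. Three independent measures each gaining 0.3 SD give 1 − (1 − 0.456)³ = 84% uncorrected, against about 66% with FDR over those three and about 40% with FDR over 12.
- A reader might infer that false success is likely. The documents give no practice effect for these tests, for people with Down syndrome, or for a 16-week gap. At 0.1 SD or less the chance is 12% or lower under the base assumptions. The supported claim is that practice alone can meet the endpoint.
- A reader might infer that data already collected could separate practice from drug. KBIT II and PPVT 5 are controls for development and vocabulary, and their practice effect may differ from that of reaction time or memory tasks. The Aim 4 section also introduces the whole list, these two included, as measures that JAK inhibition might affect. A target gain larger than the gain on these two would therefore not show a drug effect.
- The week-40 testing does not help either. Extension participants are selected, partly on skin response and study-doctor discretion, and remain on tofacitinib. A plateau after week 16 fits both exhausted practice and a saturated drug effect.

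**Conclusion.** The point holds in a limited form. As written, a significant FDR-corrected improvement on one measure at a single retest is declared a success and read as an effect of tofacitinib, although the comparison cannot exclude practice as the whole explanation. The wording also lets a control measure satisfy the rule.

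The size depends on an unknown. With an inert drug, the chance of declared success runs from about 2.4% with no retest gain to 12%, 37% and 71% if all 12 measures gain 0.1, 0.2 or 0.3 SD of change, and is about 27% if only two gain 0.3 SD. These figures assume 40 completers, change-score correlation 0.3 and Benjamini-Hochberg over 12 measures. The inference problem itself does not depend on them. Because the endpoint is tertiary and exploratory, this is a correction the sponsor should make, at the minor end, and it does not touch the primary endpoints.

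**What to change.** 1. Reword hypothesis 6 and the success definitions in section IV.C (Aim 4) and section VII (Aim 4) as improvement from baseline at 16 weeks that is not attributable to tofacitinib on this comparison alone. Bring the section VII method sentence into line. Add practice effects as a named limitation in the Aim 4 part of section VI.
2. Take KBIT II and PPVT 5 out of the any-one rule, leaving 12 − 2 = 10 measures that can count. Report change on these two beside the target measures as descriptive context, without a pass/fail threshold.
3. Optionally, report week 16 to 40 change in Extension participants descriptively, stating that they are selected and still treated.

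No new visit, test or arm is needed. The cost is a more cautious claim and two fewer measures that can produce a success. These changes do not remove a practice effect; they stop it from being reported as a drug effect.

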Type. Tertiary Endpoint.

Time Frame. Baseline and 16 weeks.

Brief Description. The Cambridge Neuropsychological Test Automated Battery (CANTAB) assesses motor response time and working memory quickly and reliably in individuals with Down syndrome. The CANTAB Paired Associate Learning subdomain will be used to measure episodic learning and the Reaction Time Interval subdomain used to measure processing speed. An FDR-corrected, two-sided, paired Student's t-test will be used to determine the significance of any changes observed.

Name. Change in Science of Behavior Change Simple Reaction Time scores.

Type. Tertiary Endpoint.

Time Frame. Baseline and 16 weeks.

Brief Description. The Science of Behavior Change (SOBC) Simple Reaction Time (SRT) is used to assess the reaction time upon seeing a stimulus. An FDR-corrected, two-sided, paired Student's t-test will be used to determine the significance of any changes observed.

Name. Change in NEPSY II scores.

Type. Tertiary Endpoint.

Time Frame. Baseline and 16 weeks.

Brief Description. The NEuroPSYchological Assessment, Second Edition (NEPSY II) is used to assess neuropsychological development. The Visuomotor subdomain will be used to measure motor development.

Name. Change in PROMIS survey tools of quality of life.

Type. Tertiary Endpoint.

Time Frame. Baseline and 16 weeks.

Brief Description. The NIH Patient-Reported Outcomes Measurement Information System (PROMIS) tool is a rigorously tested patient reported outcome (PRO) measurement tool that uses recent advances in information technology, psychometrics, and qualitative, cognitive, and health survey research to measure PROs that have a major impact on quality-of-life across a variety of chronic diseases. The Anxiety, Depression, and Applied Cognitive General Concerns Short Forms will be used, as well as the Positive Affect Pediatric Short form, to assess general quality of life. A two-sided, paired Student's t-test will be used to determine the significance of any changes observed.

B. Description of Population to be Enrolled:

We will enroll adolescents and adults (age 12-50) with DS and one or more active immune skin conditions, including AD, AA, HS, psoriasis, and vitiligo (see *Preliminary Studies Figure 1*). Additional immune-driven skin conditions may also be included at the discretion of our dermatologists. Our specific inclusion and exclusion criteria are:

Inclusion Criteria

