While not all affected cognitive skills may be increased in a measurable sense by JAK inhibition, the individual's or caregiver's perception of overall quality of life may change independent of changes in the cognitive measures proposed, either due to changes in cognitive processes not assessed as part of our trial or improvement in skin conditions as a result of treatment with a JAK inhibitor. Therefore, we will assess quality of life at baseline and again at the conclusion of treatment (16 weeks), and 40 weeks for those in the Extension Arm, using the following PROMIS metrics available through the NIH Toolbox, which are appropriate for individuals with special needs (127, 128):

- a) Emotional Distress-Anxiety Short Form 4a
- b) Emotional Distress-Depression Short Form 4a
- c) Cognitive Abilities Short Form 4a
- d) Positive Affect Short Form 4a

We define success of this endpoint as statistically significant improvement in any NIH PROMIS tool between baseline and 16 weeks as defined by a two-sided, paired Student's t-test.

D. Specific study activities implemented during COVID-19.

The following additional measures will be implemented by the study team as necessary to comply with current local guidelines during the COVID-19 pandemic. These measures are subject to change in response to State, local, and University regulations and guidance as the pandemic progresses. If any measure conflicts with direction given in this protocol or any other study document, the COVID-19-specific measure listed here will prevail.

Precautionary and Informative Measures.

- 1) The informed consent form has been updated to explain potential additional risks and benefits of study participation during COVID-19.
- 2) Study coordinators will ask participants and their study partners a series of COVID-19 screening questions during the Pre-screening phone interview to ensure they have no symptoms of and have not been in recent contact with someone with COVID-19. Coordinators should refer to the University's most recent Clinical Research Reconstitution Plan for appropriate screening questions, which can be found on the University's Weekly Update on Research Reconstitution webpage (<https://www.cuanschutz.edu/coronavirus/research-guidance/updates>). Anyone who positively answers any COVID-19 screening questions will have their study visit rescheduled.

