Method: This Aim includes exploratory tertiary endpoints to determine the impact of Tofacitinib treatment on cognitive outcomes in people with DS using cognitive assessments and their subdomains. For example, for Leiter 3 subdomains, we will employ a Wilcoxon signed-rank test (matched pairs) with which we have 80% power to detect an effect size of 0.32 with an FDR-corrected p-value less than 0.05, as calculated by G*Power software. For CANTAB subdomains, we will employ two-sided, paired Student's t-test comparing baseline and 16 weeks of treatment, we have 80% power to detect an effect size of 0.45 with an FDR-corrected p-value less than 0.05, as calculated by G*Power software.

Tertiary Endpoint: Change in PROMIS surveys of quality of life.

Endpoint Definition: A statistically significant improvement in any one or more of the NIH PROMIS tools employed between baseline and 16 weeks as defined by a two-sided, paired Student's t-test.

Method: Efforts in this Aim also include the NIH-developed PROMIS tool for quality of life assessment. Here, we will employ two-sided, paired Student's t-test comparing baseline and 16 weeks of treatment, we have 80% power to detect an effect size of 0.45 with a p-value less than 0.05 as calculated by G*Power software.

Secondary analysis to investigate potential age- and sex-dependent effects.

Although we are unlikely to have sufficient numbers for separate analysis of effects in children versus adults or females versus males, it is possible that the effects of the study drug may differ with age and/or sex, potentially reducing our power to detect significant differences in endpoint measures. To address this issue, we will conduct a series of secondary analyses, which would not affect the definition of the endpoints or the assessment of whether the endpoints were met or not, to investigate potential effects of age and sex as modifiers of the effects of the study drug.

Toward this end, we will use repeated measures ANOVA to test for significant interaction of outcome variables with either age (as a continuous variable) or sex. These analyses will yield p-values and estimates of the difference in effect size per unit of age, or between females and males, for each of the outcome measures. This would allow us to better interpret any potential failure to meet endpoint definitions.

VIII. Summarize Knowledge to be Gained:

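### The tertiary PROMIS endpoint is met by improvement on any one of four forms with no multiplicity correction, so its false-success chance is up to about 9.6% against 2.5% for one form

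*Combined protocol and SAP*

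**What the plan says.** **Success rule.** Hypothesis 5 (section I) is satisfied by improvement on one or more PROMIS tools. Research Methods for Specific Aim 4 says "We define success of this endpoint as statistically significant improvement in any NIH PROMIS tool between baseline and 16 weeks", by a two-sided paired t-test. The Data Analysis Plan (section VII, Specific Aim 4) says "A statistically significant improvement in any one or more of the NIH PROMIS tools employed between baseline and 16 weeks", with the same test. Its power sentence claims 80% power for an effect size of 0.45 at p below 0.05. None of these places, nor the PROMIS entry under Outcome Measure(s) in section IV, mentions FDR or any other correction.

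**Forms.** Each list has four forms: anxiety, depression, one cognition form and positive affect.
- Outcome Measure(s): "The Anxiety, Depression, and Applied Cognitive General Concerns Short Forms will be used", plus a pediatric positive affect form.
- Study Visits and Activities: "Cognitive Applied Cognitive General Concerns Short Form 4a, and Pediatric Positive Affect Short Form 4a will be administered", alongside the anxiety and depression forms.
- Research Methods for Specific Aim 4: "Cognitive Abilities Short Form 4a", and a positive affect form not labelled pediatric.

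The Data Analysis Plan names no PROMIS forms, so it does not settle the difference.

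**Comparable families.** The kynurenine endpoint (one or more of three values) carries FDR in the outcome list, the Aim 2 methods and the Data Analysis Plan. The cognitive endpoint (any one measure) carries FDR in the Aim 4 methods. In the Data Analysis Plan for Aim 4, the CANTAB power sentence uses an FDR-corrected p-value for the same 0.45 effect size; the PROMIS sentence does not.

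**The concern.** An any-one rule gives the endpoint four chances to succeed. With each form tested at an unadjusted 0.05, the chance that at least one shows significant improvement when nothing has changed exceeds the chance for a single form. The plan recognises this for its kynurenine and cognitive families and gives no reason for treating PROMIS differently. At stake is the quality-of-life half of Specific Aim 4, which has its own hypothesis: it could be reported as met on one chance result out of four.

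The naming difference adds to this. If the cognition form is not the same in the outcome definition and in the section that defines success, the set of four tests is not fully fixed on paper.

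**Working it through.** **Inputs.** Four forms (all three lists). Two-sided paired t-test, p below 0.05, effect size 0.45, 80% power (Data Analysis Plan, Specific Aim 4). The PROMIS power sentence gives no sample size; 40 completers is taken from the recruitment section. The correlation between forms is not in the documents and is assumed to range from 0 to 0.9.

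**Step 1: reproduce the stated power.** Paired t-test, n = 40, d = 0.45, noncentrality 0.45 × √40 = 2.85, 39 degrees of freedom, two-sided 0.05. The exact noncentral-t power is 79.3%, and the effect detectable with exactly 80% power is 0.454. The stated 80% therefore reproduces, for one form at an uncorrected 0.05.

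**Step 2: false success for one form.** Success requires improvement, so only one tail of the two-sided test counts: 0.05 / 2 = 2.5%.

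**Step 3: false success for any one of four, independent forms.** 1 − (1 − 0.025)^4 = 1 − 0.975^4 = 9.6%.

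For a significant change in either direction the corresponding figure is 1 − 0.95^4 = 18.5%, but that counts significant worsening.

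**Step 4: correlated forms.** Simulation of four equicorrelated paired t-tests, n = 40, no true change, 200,000 runs per row:

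| Correlation | Any significant improvement, uncorrected | Any significant change, uncorrected | Any significant improvement, with FDR |
|---|---|---|---|
| 0 | 9.6% | 18.5% | 2.6% |
| 0.3 | 8.8% | 17.5% | 2.4% |
| 0.5 | 7.8% | 15.7% | 2.3% |
| 0.7 | 6.6% | 13.1% | 2.1% |
| 0.9 | 4.7% | 9.5% | 1.8% |

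FDR here is Benjamini-Hochberg across the four forms at 0.05. The uncorrected inflation over 2.5% runs from 9.6 / 2.5 = 3.8-fold (independent) to 4.7 / 2.5 = 1.9-fold (correlation 0.9).

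**Step 5: cost in power.** The strictest FDR step is 0.05 / 4 = 0.0125. At n = 40 and d = 0.45, power at 0.0125 is 59.3%. The effect detectable with 80% power is 0.55, and 59 completers would be needed to detect 0.45. This is the worst case, in which only one form changes. In simulations of the any-one rule with FDR (40,000 runs per setting, correlations 0 to 0.9), power is about 59% to 61% if one form shifts by 0.45, 69% to 85% if two do, and 77% to 98% if all four do.

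**The case against.** **The endpoint is tertiary in an open-label, proof-of-concept trial, so error control is optional.** The rank does limit the consequence: no primary or secondary endpoint is touched. Labelling PROMIS descriptive would also be defensible. But the plan sets a formal significance rule for success here, and it corrects other tertiary families with the same kind of rule.

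**PROMIS is not the only gap.** This is fair. The autoantibody success definitions omit FDR, although the outcome list states it. The cognition definition in the Data Analysis Plan attaches FDR only to the Wilcoxon test. The secondary skin endpoint, also met by one or more metrics, has no correction. The contrast therefore rests on the kynurenine and cognitive families, not on uniform practice.

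**A reader might infer that the false-positive chance is about 19% instead of 5%.** The documents do not support that. The 18.5% needs independent forms and counts significant worsening, whereas the endpoint requires improvement. Independence is also unlikely for four reports from the same people.

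**A reader might infer that the two cognition form names leave the direction of success undefined.** That goes too far. Improvement fixes the direction once the form is known, and the documents do not describe the scoring of either form. The outcome list and the visit schedule also agree with each other; the Aim 4 list is the outlier. The missing pediatric label may be shorthand. What stands is a naming inconsistency to reconcile.

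**Conclusion.** The concern holds for the missing correction. With no true mean change, the PROMIS endpoint has a false-success chance of at most about 9.6% under independence, and about 5% to 9% at assumed correlations of 0.9 to 0.3, against 2.5% for a single form. These figures take 40 completers and equal correlation between the forms. They cover chance only, not improvement from other causes in an uncontrolled trial. The power sentence is right for a single uncorrected test and would not carry over to an FDR-corrected one. The form-name difference is real but close to clerical. The impact is confined to the tertiary quality-of-life claim.

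**What to change.** 1. State Benjamini-Hochberg FDR across the four PROMIS forms in the outcome entry, in the Aim 4 success definition and in the Data Analysis Plan.
2. Restate the PROMIS power sentence with n = 40: 80% power at 0.45 applies to one form at an uncorrected 0.05. At the strictest FDR step (0.0125, where only one form changes), power at 0.45 is about 59% and the detectable effect about 0.55.
3. Reconcile the cognition and positive affect entries in the Aim 4 list with the forms that the outcome list and the visit schedule say are used, so that all three carry the same four names.

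The cost is wording and a less favourable stated power. No visit, assessment or participant number changes.
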